Perceptual Mapping Survey Analysis and Vector Message Modeling. We will be responsible for the analysis of quantitative data from the survey to construct perceptual maps. These maps will be created using multidimensional scaling (MDS) software developed based on the Galileo system (The Galileo Company, 2018). Input associations among the risks/benefits are derived from the inter-item correlations. The software then performs a metric MDS analysis and produces graphic arrays of the distances among the elements to produce a 3-dimensional map (Figure B). A percentage of explained variance is calculated as an index of the explanatory power of the map, showing validity of the method. The software is highly valid; if you enter distances between American cities into the program, a map that shows the cities in proper relative positions to each other, including longitude and latitude, is constructed with very little error (SSTRESS = .003). Possible differences in perceptual maps by subgroup will be assessed using k-mean cluster analyses. This “segmentation”, usually by psychographic variables such as perception variables or demographics (gender, age etc.), is important to understand potential perceptual differences by segment. Should differences exist, maps will be generated separately for subgroups to assess whether significant differences would impact message design and incorporated into the *SAFE program*. Surveying 150-200 people with ASD and IDD should be adequate to do this sub-analysis if needed.

Once perceptual maps are constructed, we will conduct vector analyses to design messages that optimize the fit between people with ASD’s perceptual maps and the *SAFE program* intervention content. These messages will be embedded in the intervention to help people with ASD and IDD make positive, protection decisions about measures that will reduce their risk of IAD transmission. To do this, the software

SAFE Protocol

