determines optimum strategies to emphasize in a message, including both the positive and negative attributes that should be moved and where in the space they should be repositioned to “pull” the group (see dotted lines in Figure B) toward the behavior (in this case, mask wearing). Mathematically, this defines the “target vector”. This is then used to create message strategies to use in an intervention. For this study we will construct maps with multiple targeted vectors, including mask wearing, social distancing, and hand washing/hand sanitizing. While the construction of the message is left to the researcher, the content of the messages is made clear by the modeling. Once these messages are constructed, we will integrate them into the existing **SAFE program** intervention and develop processes to evaluate fidelity to the intervention. We will then “concept test” these with our advisory board to assess salience, acceptability and understanding.

Concept testing. To confirm whether the mapping strategies are salient to individuals with IDD and/or ASD, we will conduct concept testing with participants including working individuals with ASD (n=10) and IDD (n=10), vocational rehabilitation staff (n=20), and the project Advisory Board (n=20). The project Advisory Board is made up of 10 stakeholders including working individuals with ASD, family or caregivers, researchers and staff or administrators from employment service providers. We will develop a testing interview guide based on the Feedback Sessions Toolkit⁸⁰ for testing health communication messages. These groups will assess salience, understanding and acceptability. All interviews will be audio-recorded and analyzed. Once these messages are constructed study staff to integrate messages into the **SAFE program** content.

We will collect data using quantitative and qualitative interviews. We will use surveys to obtain demographic, general COVID-19 knowledge, self-advocacy/self-determination and workplace safety information. We will conduct qualitative interviews to determine acceptability and feasibility of intervention. Participants will be asked to discuss their experiences during the intervention specific to their assigned intervention group.

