A member from the research team will then contact interested individuals to set up a convenient meeting time and place for the **SAFE** program training. These meetings will occur remotely or in a private location convenient to the participant. The **SAFE** program course training will occur in small group settings or individually. The course trainings will occur 2-3 times per week for between 45-60 minutes. An appropriate curriculum has been developed by Temple University Researchers and Occupational therapy students based on many qualitative interviews, research of proper education methods, and COVID-19 practices. The curriculum is based on a series of classes designed to create an understanding of best practices and behaviors to prevent the spread of COVID-19 in the workplace. The curriculum will be adapted to meet the needs of this project and study population. The course will provide instruction in the following areas: 1) COVID-19 and how it spreads 2) PPE and How to use it properly 3) Social Distancing 4) Community Participation 5) Employment 6) Self Efficacy.

Participants will complete the **SAFE** program sessions remotely or in person in a private, quiet and convenient setting.. Participants will be randomized into two treatment arms and a control group. The first treatment arm will receive the **SAFE** program implemented through a staff training model. The second group will receive the program using a peer support model. The control group will continue to receive their standard vocational rehabilitation supports.

Training of the **SAFE** program will occur remotely or person by staff who are trained within our research team or we will implement it in collaboration with staff or a peer specialist remotely as part of their current services. If it is in person it will be implemented at their vocational rehabilitation centers or places of employment. Research staff will be available to support the process after the training is complete.

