PROMIS General Self-Efficacy Item Bank. This measure assesses a person’s belief in their capacity to manage daily stressors and have control over meaningful events. Participants will complete the 10-question tool which is designed for people 18 years and older. It has established acceptable reliability and validity.⁸¹ The responses are on a 5 point scale from “I am a little confident” (1) to “I am very confident” (5) with higher scores reflecting greater general self-efficacy. A total standard T-score will be used to analyze the data.

VocFit Safety Subscale. The VocFit is an assessment tool used to measure the best fit for a worker with a job.⁸ The tool was specifically developed for individuals with developmental disabilities and has strong psychometric properties for this population.⁸² The VocFit safety subscale consists of 8 questions asking to what degree the participant demonstrates the ability to engage in safety protocol at their employment. The tool identifies the degree to which the participant is able to follow safety protocols and precautions in their work setting. The response options include “high”, “some”, and “low”.

Workplace Health and Safety Self-Advocacy Scale (WHSSS). This measure was adapted from employment-centered items on the Self-Determination and Self-Advocacy Questionnaire, which assesses the degree of self-advocacy in the workplace as reported by staff and self-reported by participants. The measure has ten questions and takes 5-10 minutes to complete. The modified WHSSS assesses the skills used to advocate for preventative practices for IADs in the workplace and the degree to which the person uses these skills. The response options range from “none of the time” (1) to “all of the time.”

Perceptual Survey Items. To assess perceptions of IADs and protective behaviors, we will utilize the perceptual mapping items developed in the formative phase. These will be determined at baseline and the one-month follow-up to see if perceptions have changed based on intervention content. We will be able to compare perceptual maps of interventions groups to see if specific messaging affected the relationship between the group and the target protective behavior.

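### Comparing perceptual maps between the trial arms cannot show an effect of specific messaging, because the messages are part of the SAFE program that both treatment arms receive and control does not

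*Combined protocol and SAP*

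**What the plan says.** All the relevant text is in section 9 of the combined protocol and SAP.

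- **Measures, Perceptual Survey Items.** The items come from the formative phase. On timing: "These will be determined at baseline and the one-month follow-up to see if perceptions have changed based on intervention content". The next sentence says the team can "compare perceptual maps of interventions groups to see if specific messaging affected the relationship between the group and the target protective behavior".
- **Perceptual Mapping Survey Analysis and Vector Message Modeling.** The messages come from the vector analysis, and their destination is the program: "These messages will be embedded in the intervention to help people with ASD and IDD make positive, protection decisions". Further on: "Once these messages are constructed, we will integrate them into the existing" SAFE program. The vectors aim at mask wearing, social distancing and hand hygiene.
- **Procedures, description of the arms.** "Participants will be randomized into two treatment arms and a control group". The first treatment arm receives SAFE "implemented through a staff training model". For the other: "The second group will receive the program using a peer support model". For control: "The control group will continue to receive their standard vocational rehabilitation supports". The course content listed there includes correct use of PPE and social distancing.
- **Data Analysis.** ANOVAs within and between groups are planned for the outcome measures. No separate method is given for comparing maps between arms.

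**The concern.** The Perceptual Survey Items sentence links a comparison (maps between groups) to a conclusion (that particular messages changed how the group stands toward a protective behavior). A between-arm comparison can support that conclusion only if the arms differ in the messages and in nothing else that matters. Here the messages travel with the program, so the two SAFE arms differ in who delivers it, and SAFE differs from control in everything the program contains.

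What is at stake is the wording of a conclusion. A peer-staff difference in the maps could be credited to messaging when it reflects delivery. A SAFE-control difference could be credited to messaging when ordinary instruction and role play on the same behaviors would explain it equally well.

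**Working it through.** **1. What each arm receives.** Let m be the mean perception score under standard supports, S the effect of the SAFE curriculum and contact without the messages, P the added effect of peer rather than staff delivery, and M the effect of the messages. From the description of the arms:

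| Arm | Curriculum | Peer delivery | Messages | Mean |
|---|---|---|---|---|
| Control | 0 | 0 | 0 | m |
| SAFE, staff | 1 | 0 | 1 | m + S + M |
| SAFE, peer | 1 | 1 | 1 | m + S + P + M |

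The equal M in both SAFE arms is an inference from the messages being placed in the one program that both arms receive. The documents do not state it outright.

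**2. What the contrasts estimate.**

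- Peer − staff = (m + S + P + M) − (m + S + M) = P. M cancels.
- Staff − control = S + M.
- Peer − control = S + P + M.

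There are four unknowns and three arm means. The 3 × 4 design matrix has rank 3. P is estimable and the sum S + M is estimable. M alone is not, and neither is S alone. A larger sample or another way of scoring the maps does not alter the rank.

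**3. If the messages differed by arm.** With M_s for staff and M_p for peer, peer − staff = P + (M_p − M_s). The message difference is then confounded with delivery, so the stated conclusion still does not follow.

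**4. Change from baseline.** Let T be the change over the month that would occur without SAFE. Change within the staff arm = T + S + M, and within the peer arm = T + S + P + M. Subtracting the control arm's change removes T and returns to the contrasts in step 2.

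**5. Completers per arm.** The inclusion criteria give 120 recruited and 20% attrition: 120 × 0.8 = 96, which reproduces the stated final sample. The randomization text gives 40 per group: 40 × 0.8 = 32 per arm, so 64 in the two SAFE arms together and 32 in control. (The Phase 1 recruitment text instead names 120 with ASD and 120 with IDD. I use 120 in total because the inclusion criteria and the randomization text agree on it.)

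**6. What the estimable package contrast could detect.** The documents give no SD, correlation, effect size, alpha or power for these items. Assume one 0 to 10 statement, SD 2.5, baseline-to-follow-up correlation 0.5, two-sided alpha 0.05, and the same shift in both SAFE arms.

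- Residual SD after baseline adjustment = 2.5 × √(1 − 0.5²) = 2.165.
- Standard error = 2.165 × √(1/64 + 1/32) = 0.469.
- Shift of 1 point: 1 / 0.469 = 2.13, power about 56%.
- Shift of 2 points: 2 / 0.469 = 4.27, power about 99%.

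These figures are for S + M, the package, on a single statement. They are not power for messaging and not power for a whole map.

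**The case against.** The strongest case for the plan is that the sentence is permissive (the team will be able to compare) and does not stand alone. The sentence before it plans change from baseline to the one-month follow-up, the ANOVAs are within as well as between groups, and the wording does not clearly exclude control. The vector modeling also states which attributes should move and in what direction, so movement along those vectors could be read as message-specific. Finally, none of the three research questions concerns messaging, and the third asks directly about peer versus staff, so comparing those arms has its own purpose.

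Much of this stands, and it limits the point. A reader might infer that messages which worked equally in both arms would leave the trial with a null result and make the formative mapping look wasted. The documents do not support that. It would follow only if peer versus staff were the sole analysis, and change over time is also planned. A simulation with equal shifts in both SAFE arms would reject about 5% of the time for peer versus staff, but that result is built into its assumption and measures no harm. Nor is it certain that the two arms hear identical messages: the formative work also refines peer-support strategies, and it allows perceptual subgroups to affect message design. Variation by subgroup would not be randomized, however, so it would not rescue the inference.

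What does not stand is the idea that the wider readings recover a messaging effect. Including control gives the package. Change within an arm adds time. Movement along the message vectors is suggestive only, because the curriculum teaches PPE use and social distancing, which overlap with the behaviors the vectors target.

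**Conclusion.** The point holds as one of attribution. No contrast between the three arms, and no within-arm change, isolates the effect of specific messaging. Peer versus staff gives delivery mode, and SAFE versus control gives the whole program. This rests on the messages being part of the SAFE program as given to both treatment arms. That is the natural reading of the text, and step 3 shows the conclusion survives if it is wrong.

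It should not be read as saying that the perceptual data are uninformative or that the trial needs another arm. The package effect and the delivery effect are both estimable from the planned design. The power figures of about 56% and 99% are illustrative, depend on the assumed SD and correlation, and describe the package effect.

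Severity is minor. Messaging is not one of the three research questions, and no decision rule depends on these items. As written, though, the sentence promises a conclusion that the comparison cannot deliver.

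**What to change.** Replace the sentence under Perceptual Survey Items with the following content.

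1. The main perceptual comparison is both SAFE arms combined versus control at the one-month follow-up, adjusted for the baseline score, on the statements tied to the message vectors. The list of those statements is fixed when the messages are finalised. The result is reported as an effect of SAFE as a whole.
2. Peer versus staff on the same items is reported as evidence on delivery only.
3. Optionally, as exploratory support, test whether the SAFE-minus-control shift is larger on targeted than on untargeted statements. State beside it that this does not isolate messaging, because the curriculum also teaches PPE use and social distancing.

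The text should also say explicitly that control participants complete the perceptual items at both time points. The Procedures already describe pre-test and post-test collection for all outcome measures and exclude no arm.

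The cost is revised wording, one prespecified contrast and a short list of statements. No new arm, participant or instrument is needed. The downside is a narrower claim: the trial could report that SAFE shifted perceptions, but not that the messages did.

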If the participant is assigned to the staff intervention support staff will be contacted with an email or phone call. Staff members will be required to complete human subjects training. Researchers will obtain informed consent for all participants. During the first contact made with participants, written information will be provided remotely using Zoom/FaceTime or in person to all participants explaining the following in simple terms: 1) the criteria for participation, 2) the purpose of the research and the procedures involved, 3) the subject's right to withdraw at any time without penalty of any sort, 4) potential benefits to the subject, 5) potential risks, 6) assurance of anonymity, and 7) terms of remuneration. All research staff will complete training about the informed consent process prior to consenting subjects. The information described above will be reviewed and any questions answered. Participants will be obtained signed or a printed signature box used for signature when electronic signatures are unable to be obtained for consent either in person or virtually.

We will collect data from young adults or transitional aged-youth with ASD or IDD to determine the efficacy and feasibility of the intervention. Recruitment occurs through the sites identified in the participant recruitment section of this proposal. Participants interested in the study will contact the primary investigator or research staff who will schedule an initial physical or virtual meeting at a place and time convenient for the participant to determine inclusion and obtain consent/assent. Participants are randomly assigned to either peer-support intervention, staff intervention or a control group. We will randomize in blocks of 12 (4 to each group) until we reach the targeted number of 120 or

SAFE Protocol

40 participants in each group. Pre-test and post-test measures will be administered by researcher staff prior to the start of the intervention (Pre-test) and at the end of the intervention 4 weeks (Post-test). Key stakeholders, including the participants and interventionists (occupational therapists and peer mediators), will complete qualitative interviews at the end of the intervention period for each participant. The information gathered will determine acceptability and feasibility of intervention. Participants will be asked to discuss their experiences during the intervention specific to their assigned intervention group.

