In Phase 2, feasibility data will be collected exclusively by the staff completing the SAFE curriculum training. They will assess how feasible and acceptable the SAFE program, including the new lesson, is for their clients or students. This phase will not involve a pilot study with participants.

c) Withdrawal of Subjects

Participation is voluntary and there is no penalty if a person chooses not to join the research study. They will continue to receive services as usual. If a person enrolls in the study and later chooses to withdraw from the study, they may do so at any time without any penalty. They can withdraw from the study by contacting the primary researcher through telephone or email.

d) Privacy & Confidentiality

The study team has placed safeguards to maintain the confidentiality of participants' personal information.

Phase 1: Personal information will be kept electronically in password protected files and hard copies will be stored in locked cabinets at the TU Collaborative on Community Inclusion, located at [name]. Except for the legal requirements described below, only research staff will have access to personal information. By law, however, the Temple University Institutional Review Board (IRB), National Institute of Disability, Independence Living and Rehabilitation Research (NIDLRR), the Office for Human Research Protections, and the Philadelphia Department of Public Health IRB, are required to have access as well. Study files will be kept for seven years after the last publication of the data. Any information about child abuse or intent to harm oneself or others will be reported to authorities, as is required by law. Efforts will be made to limit personal information access to people who have a need to review this information.

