All information gathered about participants for this study is confidential, except as may be required by law. For example, confidentiality would not be honored if a person expressed a current plan to harm themselves or others, or if they report they have committed child abuse or neglect. Completed interviews will contain a coded identification number to prevent loss of confidentiality. Confidentiality of data files will be achieved by separating code numbers from individual identifying information. Information taken about participants will be kept electronically only in password protected files on an encrypted network and hard copies will be stored in locked cabinets. Research investigators will be the only people with access to this data, with the exception of authorized representatives of the Temple University Institutional Review Board (IRB), who are required to have access by law. For phase 2, No hard copies will be retained. If a person is unable to sign electronically and a physical signature is required, the document will be scanned, stored as a PDF in the confidential digital system, and the hard copy will be destroyed. Protected health information will not be collected for participants during the qualitative interviews. Participant contact information will always be kept separate from the data. Participant information will be password protected and stored on an encrypted network. Whenever feasible, identifiers will be removed from study-related information. All published reports will contain data reported either in aggregate form (where no individual responses can be identified), or in composite individual examples that are constructed so that identification is impossible.

During the consent process, individuals will be informed that they can stop the interview at any time should they feel uncomfortable. They will also be told that they do not have to answer any question that they do not want to answer. All data will be assigned a number for data management purposes. Data collected from participants will only be kept electronically in password-protected files on an encrypted network. Research investigators will be the only people with access to this data, with the exception of authorized representatives of the Temple University Institutional Review

SAFE Protocol

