All adult participants in the study will provide informed consent. Consent will be obtained remotely and through electronic signatures until it is safe to meet one on one with participants. Individuals will meet remotely with research staff to review and obtain informed consent in REDCAP via a zoom meeting or comparable. The primary investigator or a research assistant will obtain informed consent and when needed assent when possible for each participant. The research assistant will obtain training in the consent process to ensure that there is no coercion and proper procedures are followed. During the first contact made with adult participants (either in person, electronically, or over the phone), written information will be provided in person or through electronic formats. Researchers will explain the following in simple terms to all participants: 1) the criteria for participation, 2) the purpose of the research and the procedures involved, 3) the subject's right to withdraw at any time without penalty of any sort, 4) potential

SAFE Protocol

benefits to the subject, 5) potential risks, 6) assurance of anonymity, and 7) terms of remuneration. Although it is anticipated that many participants will be able to provide informed consent, a process for obtaining informed consent from a legally authorized representative (i.e. parent, caregiver, or another individual with legal guardianship) and assent from the participant will be used if the individual is under guardianship or not able to provide consent. Some participants may not have a legally authorized representative. In those cases investigators will take special care for all participants who have an intellectual or developmental disability to ensure that participants understand the consent process by going over the information slowly with them and asking them to repeat back to the investigator each aspect of the consent process. Accommodations will be made to ensure that communication between the participant and the investigator is as clear as possible (i.e., use of sign language interpreter, assistive communication devices as needed).

The following format will be used to obtain informed consent/assent process and to assess each potential participants understanding of that to which they are agreeing.

- (A) Each potential participant will be provided with a copy of the informed consent/assent form and asked to read the form.

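### Staff are told to assure every participant of anonymity, but the plan describes a confidential study with coded data, outside access and mandatory reporting

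*Combined protocol and SAP*

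**What the plan says.** The instruction appears twice in nearly the same words. Section 9, under Study Procedures and Data Analysis, lists seven topics to be explained to all participants at first contact. Section 14, Informed Consent, repeats the list. In both it closes with "5) potential risks, 6) assurance of anonymity, and 7) terms of remuneration". Neither list has an item on confidentiality or on when it can be broken.

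Section 9 d), Privacy & Confidentiality, describes something different:

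- **Coding.** "Completed interviews will contain a coded identification number to prevent loss of confidentiality" and "Confidentiality of data files will be achieved by separating code numbers from individual identifying information".
- **Identifiers.** "Whenever feasible, identifiers will be removed from study-related information". Contact details are held apart from the data.
- **Access.** Bodies outside the research team, including the university IRB and, by phase, a federal funder, a federal oversight office, a city IRB or the state health department, may see personal information.
- **Reporting, Phase 1 and Phase 2 paragraphs.** "Any information about child abuse or intent to harm oneself or others will be reported to authorities, as is required by law".
- **Reporting, later general paragraph.** After stating that information is confidential subject to legal requirements, it gives as an example that confidentiality would not hold "if a person expressed a current plan to harm themselves or others, or if they report they have committed child abuse or neglect".

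Section 14 then sets nine comprehension questions. The sixth asks whether the study team will share the participant's information with others, and the seventh asks how it is kept private.

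**The concern.** Anonymous means that nobody, including the study team, can tie a response to a person. Confidential means that the team can, and undertakes to restrict who else does. The plan describes the second and instructs staff to promise the first. The audience is adults with ASD or IDD, whom section 6 calls a vulnerable population, and some of them consent through a representative.

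Two things are at stake. One is the accuracy of what participants are told before they agree to be recorded and to answer personal questions. The other is the protocol's own test of understanding, because the item that staff are to explain points to a wrong answer to one of the questions used to decide whether a person may enrol.

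**Working it through.** No figure is involved, so the check sets the relevant paragraphs side by side.

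**Step 1: could the study be anonymous?** Each feature below is enough to make participants identifiable to the team or to others.

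| Feature | Where | Consequence |
|---|---|---|
| Signed consent, on paper or electronically | Section 9, procedures; section 14 | The team holds names |
| Pre-test and post-test on the same person | Section 9, procedures | Records must be linked within a person |
| Audio-recorded one-to-one interviews | Section 9, Measures | The voice is captured |
| Code numbers kept apart from identifiers | Section 9 d) | Coded, not anonymous |
| Removal of identifiers only where feasible | Section 9 d) | Some may remain |
| Oversight access to personal information | Section 9 d) | Others can see identity |
| Reporting of certain disclosures | Section 9 d) | Identity may have to be revealed |

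That the data can be linked back is partly an inference. The plan does not describe a retained key in so many words, but it keeps both codes and identifiers and does not say that the link is destroyed. The other rows do not depend on this inference.

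**Step 2: does the wrong word reach the enrolment decision?** Under section 9 d), the correct answer to question 6 is yes, in defined circumstances: oversight bodies have access and some disclosures are reported. A participant who relied on an assurance of anonymity could reasonably answer no. In Phase 1, a person who cannot answer accurately is not enrolled unless a parent or legal representative can consent. In Phase 2, a person unable to answer is excluded. So a participant could be marked as not understanding because of what staff were told to say.

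**Step 3: is there one account of reporting for staff to give?** There are two wordings. The Phase 1 and Phase 2 paragraphs are identical to each other.

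| Topic | Phase 1 and Phase 2 paragraphs | Later paragraph (examples) |
|---|---|---|
| Harm to self or others | Intent | A current plan |
| Child abuse | Any information | Participant reports having committed it |
| Neglect | Not named | Named, with child abuse |

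The wordings differ in scope. Both defer to the law, and the second is introduced as an example, so the difference falls short of a strict contradiction.

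**Step 4: how many people does it reach?** Both lists are addressed to all participants. For the randomised pilot, the procedures section gives three groups of 40, that is 3 × 40 = 120. The interview, survey and focus-group participants are additional.

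**The case against.** The best defence is that the seven points are topic labels, not a script. Section 14 has each section of the consent form read aloud to participants with disabilities. The online survey's visible consent highlights confidentiality. Questions 6 and 7 show that sharing and privacy are meant to be covered. Section 7 trains staff in privacy, confidentiality and the reporting of unanticipated problems, with weekly meetings and supervision. The word may also be loose shorthand for the undertaking that published reports will not identify anyone. This limits how much can be claimed about what participants hear. It does not remove the instruction, which appears twice and names the wrong protection.

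A reader might infer more than the documents support:

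- **That the reporting rules contradict each other, so two interviewers would act differently on the same disclosure.** The narrower wording is an example under a general legal exception. It does not override the broader statement. Any tally of agreement across scenarios depends on which are chosen, and both wordings cover a participant who reports having committed child abuse.
- **That mistreatment of an adult participant is excluded from reporting.** It is not named, but the general legal exception does not rule it out, and what the law requires is outside the documents.
- **That there is no route for handling a disclosure.** No single recipient is named, but the training and supervision in section 7 exist. More detail there would be a preference, not the correction of an error.

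**Conclusion.** The point holds for the anonymity item. Both lists tell staff to assure something that section 9 d) makes untrue, and the error bears on a comprehension question that counts towards enrolment. The different wordings on reporting are a lesser matter of consistency.

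The conclusion rests on the protocol text alone. The consent and assent forms are not in the public file and may word this correctly, so it is not established that any participant has been misinformed. The effect on answers to question 6 is a plausible consequence that cannot be quantified from the documents. Randomisation, outcomes and the statistical analysis are not affected. The correction is worth making because the participants are vulnerable and the change is small.

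**What to change.** In the section 9 procedures list and the section 14 list, replace the sixth item with confidentiality and its limits, covering who has access to personal information and what is reported. Check the consent and assent forms, and the expected answers to questions 6 and 7, against the new item.

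As a secondary change, use one wording on reporting throughout section 9 d), so that intent and current plan, and any information and own report, are reconciled. The sponsor and the IRB set the thresholds. The access statements can be aligned at the same time: the phase-specific paragraphs name several bodies, while the later paragraphs except only the university IRB.

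The cost is an IRB amendment and edits to a few paragraphs. The downside is that some participants may disclose slightly less once they are told the limits.
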